8.1.1 Immunogenic Reactions

Diagnosis of an immunogenic reaction that may lead to a thrombotic event will be based on treatment-emergent positive anti- β 2GPI and β 2GPI-DI antibody titers, defined as an antibody titer of ≥ 40 U found twice on tests that are at least 12 weeks apart and/or on treatment-emergent positive anti- β 2GPI and β 2GPI-DI antibody titers > 20 U but < 40 U in combination with a treatment-emergent thrombotic or thromboembolic event (Unlu et al., 2015) by these definitions will be considered significant events. If any subject after receiving IMP seroconverts from negative to positive, with an elevated rising antibody titer at least 12 weeks apart, then all prior retention samples for β 2GPI and/or β 2GPI-DI for all subjects should be analyzed.

Subjects who develop treatment-emergent anti- β 2GPI and/or β 2GPI-DI antibody titers > 20 U following exposure to IMP will be followed closely by the investigator for thrombotic and/or thromboembolic events. These subjects will have periodic (no more than 8 weeks apart) anti- β 2GPI and β 2GPI-DI antibody titer testing until they have completed 52 weeks of treatment with IMP or until immunogenicity titers have stabilized or are declining over 3 consecutive treatment cycles (21 or 28 day cycles), whichever is later.

As shown in Figure 2:

1. Any subject who has a significant event as defined above for anti- β 2GPI and/or β 2GPI-DI antibodies while being treated with IMP will permanently discontinue treatment with the IMP. The subject will remain in the study for safety assessments up to the time of the final follow-up phone call after LTSF (see Section 7.11).
2. The occurrence of two such significant events as defined above for anti- β 2GPI and/or β 2GPI-DI antibodies will be referred to the DSMB for an urgent ad-hoc review to determine if this qualifies as a potential study-stopping event as defined above.
3. If two or more subjects treated with IMP are confirmed to meet the criteria for a significant event, as defined above, all treatments with the IMP will be discontinued until the lead investigator, the DSMB, and the FDA have reviewed all the anti- β 2GPI and β 2GPI-DI antibodies safety data for subjects enrolled. During this time, no new subjects will be enrolled. If a subject should require a scheduled infusion during this time, they will continue therapy with a commercially available preparation (CP). IMP infusions will be recommenced if approval to continue the study is given by the DSMB and FDA.
4. Any subject who becomes positive for anti- β 2GPI and/or β 2GPI-DI antibody titers, as defined above, while being treated with CP will be treated at the discretion of the Investigator in discussion with the sponsor.

The IRB/IEC and the US FDA/appropriate regulatory authority for trials outside the US will be immediately notified of any suspected ADRs involving immunogenic reactions.

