8.1 Interim Analyses and Stopping Rules for Subjects on IMP

The DSMB (see Section 8.7), Sponsor, or PI may elect to terminate the study early as defined by the clinical study agreement.

The study may also be stopped, suspended, or terminated for subjects with specific characteristics or for all subjects at any or all sites for any of the reasons described below.

As described in Section 3.1 and Section 12.5, two interim analyses will be performed, based on the following in Group 1 and Group 2:

- Testing for antibodies to β -2 glycoprotein I ($\beta 2$ GPI) and to β -2 glycoprotein I domain I ($\beta 2$ GPI-DI);

[figure not shown]
- General safety laboratory tests (hematology, chemistry, urinalysis) before Infusion and on Day 7 after Infusion;
- Hemolysis laboratory test before Infusion and at Day 2 or 3 and Day 7 after Infusion;
- Clinical hemolysis & thrombosis assessment 1 h, 24 h and 72 h after Infusion;
- D-dimers & retention sample for proteins C & S 3-4 h after Infusion;
- Adverse Event data.

The algorithm for study-stopping rules shown in Figure 2 will be followed.

- If ≥ 2 subjects showing either (a) treatment-emergent positive anti- $\beta 2$ GPI and/or $\beta 2$ GPI- DI antibody titers ≥ 40 U as defined in Section 8.1.1 or (b) treatment-emergent positive anti- $\beta 2$ GPI and/or $\beta 2$ GPI-DI antibody titers > 20 U but < 40 U in combination with a treatment-emergent thrombotic or thromboembolic event, or a combination of (a) and (b).
- If ≥ 2 subjects present with confirmed thromboembolic events, as defined in Section 8.1.2, following full work-up for thrombosis.
- If ≥ 2 subjects present with confirmed hemolytic events, as defined in Section 8.1.3, following full work-up for hemolysis.

In the event any of the above occurs, administration of IMP for all subjects will be on hold until the investigator, DSMB, and FDA have reviewed the safety data and agree to resume dosing with IMP.

Figure 2. Summary of Stopping Rules

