8.1.2 Thrombotic Events

As shown in Figure 2:

- Investigator will examine subjects for clinical signs of thrombosis (Section 6.12.2). Positive assessments will lead to a full work-up for thrombosis, as appropriate, according to the facility's standard of care. In the case that d-dimer results indicate potential thrombosis, protein C and protein S testing will be done based on Investigator evaluation (Section 6.11).
- Any subject who is diagnosed with a thromboembolic event based on clinical and laboratory assessment while being treated with IMP will permanently discontinue treatment with the IMP and will receive standard medical care. The subject will remain in the study for safety assessments up to the time of the final follow-up phone call after LTSF (see Section 7.11). All such events will be referred to the DSMB for an urgent ad-hoc review to determine if this event qualifies as a potential study-stopping event as defined above.
- Any subject who is diagnosed with a thrombotic or thromboembolic vascular event based on clinical and laboratory assessment while being treated with the commercial product will receive standard medical care and continuation in the study will be at the discretion of the Investigator. If the subject is terminated from the study, the PI will determine continued treatment for managing the disease, in consultation with the subject's treating physician and per standards of care. The subject will remain in the study for safety assessments up to the time of the final follow-up phone call after LTSF (see Section 7.11).
- If two or more subjects experience confirmed thrombotic or thromboembolic vascular events in the trial as a whole in subjects receiving IMP, the DSMB will put the study on temporary hold while an assessment is made. All treatments with the IMP will be discontinued until the investigator, the DSMB, and the FDA have reviewed safety data for subjects enrolled. During this time, no new subjects will be enrolled. If a subject should require a scheduled infusion during this time, they will continue therapy with a commercially available preparation (CP). IMP infusions will be recommenced if approval to continue the study is given by the DSMB and FDA.

The IRB/IEC and the US FDA/appropriate regulatory authority for trials outside the US will be immediately notified of any suspected ADRs involving thromboembolic events.

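### Section 8.1.1 refers significant antibody events to urgent DSMB review only at two, so the protocol text requires no prompt board review of a first titer-only event unless it is reported as an SAE

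*Protocol*

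**What the plan says.** Protocol Section 8.1.1 opens its definition with "Diagnosis of an immunogenic reaction that may lead to a thrombotic event". It recognizes two kinds of significant event:

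- **Titer-only:** a treatment-emergent titer of at least 40 U "found twice on tests that are at least 12 weeks apart".
- **Titer plus clinical event:** a titer above 20 U but below 40 U together with a treatment-emergent thrombotic or thromboembolic event.

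Item 1 takes any subject with a significant event off IMP permanently and names no DSMB step. Item 2 makes "The occurrence of two such significant events as defined above" the trigger for urgent ad-hoc DSMB review. Item 3 says that when two or more subjects "are confirmed to meet the criteria for a significant event, as defined above, all treatments with the IMP will be discontinued", pending review by the lead investigator, the DSMB and the FDA. Section 8.1 sets the same count for all three hazards: once two subjects qualify, "administration of IMP for all subjects will be on hold until the investigator, DSMB, and FDA have reviewed the safety data".

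For thromboembolic events on IMP, Section 8.1.2 says "All such events will be referred to the DSMB for an urgent ad-hoc review". Section 8.1.3 does the same for any hemolysis event on IMP. Section 8.7 has the DSMB look at individual subjects whenever a thrombotic or hemolytic event is suspected or reported, and does not name antibody events. Its other ad hoc route is for concerns raised by SAEs.

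**The concern.** The protocol treats these antibodies as a possible precursor of thrombosis, and antibody testing comes first in Section 8.1's list of what the Group 1 and Group 2 interim analyses examine. One confirmed case is serious enough to end IMP for that subject, as one hemolysis case is. Yet only the hemolysis case must go urgently to the independent board. If exactly one subject has a titer-only event, the other subjects continue on IMP and nothing in the protocol text obliges the board to look at the case promptly. A referral set at the same count as the hold gives little early warning.

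What is at stake is the timeliness of safety oversight. The primary efficacy analysis and its error rate are not affected.

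**Working it through.** **1. Trigger counts side by side**

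| Event on IMP | Urgent DSMB referral | Hold of all IMP |
|---|---|---|
| Thromboembolic (8.1.2, 8.1) | 1 | 2 |
| Hemolysis (8.1.3, 8.1) | 1 | 2 |
| Significant antibody event (8.1.1 items 2 and 3, 8.1) | 2 | 2 |

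Item 2 counts events and item 3 counts confirmed subjects. A subject with one significant event leaves IMP for good, so two events will ordinarily mean two subjects.

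**2. Which events fall in the gap**

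A significant event that includes a thromboembolic event reaches the DSMB at the first case through 8.1.2. That leaves the first titer-only event. It can reach the board quickly as an SAE, since Section 10.1.1 counts a clinically significant laboratory finding as an AE and Section 10.1.4 admits medically important events, but that depends on medical judgment.

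**3. When a titer-only event can be confirmed**

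Section 6.10 schedules on-treatment antibody tests before Infusions 2, 4 and 8 and at the LTSV.

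- 21-day cycle: Weeks 3, 9, 21 and 51. The first pair at least 12 weeks apart is complete at Week 21 (21 − 9 = 12).
- 28-day cycle: Weeks 4, 12, 28 and 52. The first such pair is complete at Week 28 (28 − 12 = 16; the Week 4 and 12 tests are only 8 weeks apart).

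The extra testing for titers above 20 U, at most 8 weeks apart, could confirm sooner. The Group 1 and Group 2 reviews used samples drawn before Infusion 2 (Week 3 or 4), which cannot establish this event, and Section 1.4 shows that both reviews were finished in 2016. The later review comes after 20 Group 3 subjects have at least 6 doses (protocol 8.7) or 6 months of dosing (SAP 6.2). It could show a case but is not triggered by one.

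**4. How often item 2 would stay silent**

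The documents state no event risk and no operating characteristics for these rules, so there is no planned figure to reproduce. The per-subject risk p of a titer-only event is assumed at 1%, 2% and 5%, with independent subjects. N is 60 (planned evaluable) or 75 (planned enrolled).

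- Exactly one event: P(X = 1) = N·p·(1 − p)^(N−1)
- At least one event: P(X ≥ 1) = 1 − (1 − p)^N

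Example, N = 60 and p = 1%: 60 × 0.01 × 0.99^59 = 0.332; 1 − 0.99^60 = 0.453; ratio 0.732.

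| N | p | P(X = 1) | P(X ≥ 1) | P(X = 1 given X ≥ 1) |
|---|---|---|---|---|
| 60 | 1% | 0.332 | 0.453 | 0.732 |
| 60 | 2% | 0.364 | 0.702 | 0.519 |
| 60 | 5% | 0.145 | 0.954 | 0.153 |
| 75 | 1% | 0.357 | 0.529 | 0.673 |
| 75 | 2% | 0.336 | 0.780 | 0.431 |
| 75 | 5% | 0.084 | 0.979 | 0.086 |

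Referring each event raises the chance of at least one urgent antibody referral by P(X = 1). At N = 75 it goes from 17.3% to 52.9% (p = 1%), 44.4% to 78.0% (2%) and 89.4% to 97.9% (5%).

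**5. What one event shows**

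The exact two-sided 95% upper limit for the true risk is 8.9% after 1 event in 60 and 7.2% after 1 in 75. A single case therefore does not establish that the risk is low.

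**The case against.** The strongest reply is that a first titer-only event already meets a substantial response. The subject stops IMP permanently. Regulators and the IRB/IEC are "immediately notified of any suspected ADRs involving immunogenic reactions". Titers above 20 U are followed closely. Section 8.1.1 requires that, when a subject seroconverts on IMP "with an elevated rising antibody titer at least 12 weeks apart, then all prior retention samples" from all subjects are analyzed. Section 6.10 states the same rule for an elevated titer without requiring it to be rising. Since antibody-positive subjects are excluded at Screening, a first titer-only event would ordinarily set off a search for a second case across the trial, and a second case holds the trial. Under Section 8.7 the DSMB also has ongoing safety review and can call for retention testing at any time. Section 10.1.6 has it review causality before database lock. A reader might infer that a first case goes unanswered; the text does not support that.

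A reader might also infer that item 2 is simply redundant. That goes too far. Item 3 requires subjects to be confirmed, so item 2 can be read as the DSMB's confirmation step before the hold, although Section 8.1 states the hold at two subjects without that step. On either reading, nothing is referred at the first event.

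A laboratory precursor may fairly have a different threshold from a clinical harm. That argument could justify a different count for the hold, but the hold count is the same for all three hazards. It does not explain why referral waits for the hold count.

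Finally, Section 8.1.1 presents its items as shown in Figure 2, which is not reproduced in the available text, and Section 8.7 places stopping rules in a DSMB charter that was not supplied. Either may already require review of a first case. This objection stands and makes the point conditional.

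**Conclusion.** The point holds as a gap in the protocol text, limited to a first titer-only event. For that event, no prompt DSMB review is required unless it is reported as an SAE.

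At an assumed risk of 1% to 2% per subject, exactly one event would occur in 33% to 36% of trials. Among trials with any such event, item 2 would never be triggered in 43% to 73%. At 5%, exactly one event occurs in 8% to 15%, because two or more become likely. These risks are assumptions, and the percentages describe how often the rule is silent. They do not measure harm.

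A reader might infer that referring each event would give rapid detection. The documents do not support that. Section 8.7 has immunogenicity samples after the pre-Infusion 2 draw tested in batches, and the definition needs two results at least 12 weeks apart. Those two features largely set when a case is found, and the referral count changes neither. The gain is therefore modest: the board sees a confirmed case at the first event instead of the second.

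Severity is low, and no efficacy result changes. It is worth doing because it is cheap.

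**What to change.** 1. Reword Section 8.1.1 item 2 so that each significant antibody event in a subject on IMP, once confirmed, goes to the DSMB for urgent ad-hoc review of whether it may be study-stopping, in line with 8.1.2 and 8.1.3.
2. In Section 8.7, add significant antibody events (8.1.1) to the sentence on DSMB review of individual subjects.
3. Check Figure 2 and the DSMB charter, and align them if they differ.
4. Keep the two-subject hold as written.

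The cost is two protocol sentences and, if needed, a matching line in Figure 2 and the charter. There are no new visits, samples or patients. The downside is at most one extra ad-hoc DSMB review before the two-subject hold applies.

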8.1.2 Thrombotic Events

As shown in Figure 2:

- Investigator will examine subjects for clinical signs of thrombosis (Section 6.12.2). Positive assessments will lead to a full work-up for thrombosis, as appropriate, according to the facility's standard of care. In the case that d-dimer results indicate potential thrombosis, protein C and protein S testing will be done based on Investigator evaluation (Section 6.11).
- Any subject who is diagnosed with a thromboembolic event based on clinical and laboratory assessment while being treated with IMP will permanently discontinue treatment with the IMP and will receive standard medical care. The subject will remain in the study for safety assessments up to the time of the final follow-up phone call after LTSF (see Section 7.11). All such events will be referred to the DSMB for an urgent ad-hoc review to determine if this event qualifies as a potential study-stopping event as defined above.
- Any subject who is diagnosed with a thrombotic or thromboembolic vascular event based on clinical and laboratory assessment while being treated with the commercial product will receive standard medical care and continuation in the study will be at the discretion of the Investigator. If the subject is terminated from the study, the PI will determine continued treatment for managing the disease, in consultation with the subject's treating physician and per standards of care. The subject will remain in the study for safety assessments up to the time of the final follow-up phone call after LTSF (see Section 7.11).
- If two or more subjects experience confirmed thrombotic or thromboembolic vascular events in the trial as a whole in subjects receiving IMP, the DSMB will put the study on temporary hold while an assessment is made. All treatments with the IMP will be discontinued until the investigator, the DSMB, and the FDA have reviewed safety data for subjects enrolled. During this time, no new subjects will be enrolled. If a subject should require a scheduled infusion during this time, they will continue therapy with a commercially available preparation (CP). IMP infusions will be recommenced if approval to continue the study is given by the DSMB and FDA.

The IRB/IEC and the US FDA/appropriate regulatory authority for trials outside the US will be immediately notified of any suspected ADRs involving thromboembolic events.

8.1.3 Hemolysis

As shown in Figure 2:

- Investigator will examine subjects for clinical signs of hemolysis (Section 6.12.2). Positive assessments will lead to a full work-up for hemolysis, as appropriate, according to the facility's standard of care.
- For all subjects, a drop of ≥ 2.0 g/dL from the pre-infusion hemoglobin level or clinical signs of hemolysis between visits will lead to a full hemolysis work-up (Section 6.9).
- Any subject who is diagnosed for a hemolysis event based on clinical and laboratory assessment while being treated with IMP will permanently discontinue treatment with the IMP and will receive standard medical care. The subject will remain in the study for safety assessments up to the time of the final follow-up phone call after LTSF (see Section 7.11). Any such event will be referred to the DSMB for an urgent ad-hoc review to determine if this event qualifies as a potential study-stopping event as defined above.
- Any subject who is diagnosed with hemolysis based on clinical and laboratory assessment while being treated with the commercial product will receive standard medical care and continuation in the study will be at the discretion of the Investigator. If the subject is terminated from the study, the PI will determine continued treatment for managing the disease, in consultation with the subject's treating physician and per standards of care. The subject will remain in the study for safety assessments up to the time of the final follow-up phone call after LTSF (see Section 7.11).
- If two or more subjects experience confirmed hemolysis events in the trial as a whole in subjects receiving IMP, the DSMB will put the study on temporary hold while an assessment is made. All treatments with the IMP will be discontinued until the investigator, the DSMB, and the FDA have reviewed safety data for subjects enrolled. During this time, no new subjects will be enrolled. If a subject should require a scheduled infusion during this time, they will continue therapy with a commercially available preparation (CP). IMP infusions will be recommenced if approval to continue the study is given by the DSMB and FDA.

The IRB/IEC and the US FDA/appropriate regulatory authority for trials outside the US will be immediately notified of any suspected ADRs involving hemolysis.

8.1.4 Other Reasons for Termination

- The safety data reviewed by the DSMB demonstrate or strongly suggest that the study treatment (or participation in the study) is unsafe.

- The protocol or conduct of the study is flawed such that the safety or rights of the study subjects may be adversely affected.
- The IRB/IEC has withdrawn approval for the study and has denied reconsideration.
- Relocation of the PI, reallocation of the PI's responsibilities, or disqualification of the PI by order of the regulatory authority
- Non-adherence to the protocol or unavailability/lack of supervision by the PI and/or inadequate resource to conduct the study.
- Clinical hold imposed by the FDA/appropriate regulatory authority for trials outside the US.

Any decision to voluntarily suspend or terminate a clinical study will be carefully reviewed and fully justified. The sponsor will notify the FDA/appropriate regulatory authority for trials outside the US and the IRB/IEC of any suspension or termination, along with justification for restarting or terminating the study as applicable.

8.2 Withdrawal Criteria and Replacement of Subjects

Subjects will be withdrawn for any of the following reasons:

- The subject withdraws consent (no justification is required);
- The subject is pregnant;
- The subject develops a condition that in the investigator's opinion makes it medically necessary that the subject not continue in the study.

After an investigator and sponsor discussion, subjects may be withdrawn for the following reasons:

- An AE that in the Investigator's or sponsor's opinion requires the subject be withdrawn from the study;
- Violation of eligibility criteria;
- Major protocol violations or deviations from the treatment plan dictated by the protocol (e.g., incorrect IMP administration);
- Lost to follow-up after all attempts at contacting the subject; and/or
- Death.

In all cases, the reasons for withdrawal will be recorded in the subject's source documentation and in the eCRF. It is possible that some subjects may become lost to follow-up during the study. Every reasonable effort will be made to contact these subjects; all available efficacy and safety data collected for these subjects will be used, even if incomplete.

8.3 Screen Failures

Subjects who do not meet the entry criteria through Baseline will be ineligible for treatment and will be deemed screen failures. Subjects who fail screening will not receive the IMP; therefore, no efficacy, safety, or PK data will be collected for these subjects, and only demographic information will be collected on the eCRF. Subjects who fail screening will be considered screened but not enrolled. Only subjects who qualify for treatment with CP/IMP will be enrolled.

8.4 Subject Identification

Subjects will be identified by a numerical code in the site master log or the site database. Prior to approaching a subject, the site must look at the general eligibility criteria of the subject as a pre-screen check to ensure that the cohort is not already fully enrolled across the study. The process will be an approval process via the CRO. Once approval has been given to enroll and in which group, the site will begin the screening process. All subjects who sign the ICF/assent will receive a Subject Identification Number according to the following format: XX-YYY (site number-subject number) to be defined in a Study-specific Operations Manual. The anonymity of subjects will be maintained insofar as is required by law in order to protect the subjects' rights to privacy. Personal identifying information may only be obtained by the Investigator or their designee to complete the requirements of the protocol, and must be kept by the Investigator in strictest confidence and may not be released unless required by law. See Section 17 for additional information regarding confidentiality.

